6.3.6 AVIVO/HealthPatch monitoring

AVIVO Mobile Patient Management System is intended to continuously measure, record and periodically transmit ECG data.

Notifiable ECG-findings (like AV-conduction abnormalities) triggered by system/patients based, as well as reportable ECG finding according to AVIVO will be summarized in frequency tables by treatment group. ECG-findings according to HealthPatch will also be summarized in frequency tables by treatment group. A table displaying the number of patients with AV-block > I° according to AVIVO/HealthPatch will be provided by treatment group. All patients with significant ECG-finding will be listed. The definition of the findings that trigger a notifiable report is in Appendices 9.1.

6.3.7 Other safety measures

The last pre-treatment safety measurement, i.e., SBP(systolic blood pressure), DBP(diastolic blood pressure), weight, body temperature, heart rate, respiration rate and electrocardiogram (12 lead ECG) will be used as “baseline value.”

When more than one value is collected at the same post-baseline visit, the value retained at that particular visit for summary statistics will be the average of the different measures reported for that visit.

For each treatment group, vital signs will be tabulated and summarized by visit for observed values and changes from baseline using descriptive statistics, as appropriate.

The incidence rates of treatment-emergent 12-lead ECG abnormalities will be tabulated by treatment group. A descriptive analysis of continuous ECG parameters and their changes from baseline by visit and treatment group will also be presented. PR interval will be summarized by visit and treatment group.

6.4 Subgroup Analysis

6.4.1 Subgroups

Subgroups are specified in Section [4.5.4](#).

6.4.2 Subgroup analysis of efficacy variables

Primary, secondary and sensitivity analyses (without imputed values) of primary efficacy variables will be performed based on key subgroups. Additionally primary efficacy variables will be descriptively summarized based on exploratory subgroups.

Secondary efficacy variables will be descriptively summarized based on key subgroups and exploratory efficacy variables will be descriptively summarized based on LVEF(%) at baseline: ≤ 40 vs. > 40 .

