10.3.2 Statistical and analytical plans

All data will be listed and all variables will be summarized by means of descriptive statistics according to their type.

Summaries by treatment group using appropriate descriptive statistics will be provided for all study variables including demographic and baseline characteristics. Summary statistics will be presented for the original data as well as for the difference to baseline. Descriptive statistics such as arithmetic mean (or geometric mean, if applicable), median, standard deviation, quantiles, minimum, and maximum will be used to summarize continuous variables. Counts and percentages will be used to summarize categorical variables. Life tables and Kaplan-Meier estimates will be used to summarize time-to-event variables. Graphical data displays may also be used to summarize the data. Confidence intervals will be provided at a 2-sided level of 90% unless otherwise stated.

For this combined proof-of-concept and dose-finding study, an overall one-sided type I error level of 5% is planned to be used. The type I error will be controlled for the primary analysis of the primary variables.

There will be no formal control of the type I error for secondary or explorative analyses of the primary variables and any analysis of other efficacy variables.

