- the expected mean effect under the placebo dose is conservatively assumed as an absolute increase from baseline of up to $\Delta = 2\%$ with a standard deviation of $\sigma = 7\%$
- while the maximum observable mean effect under neladenoson bialanate within the dose range considered is assumed as an absolute increase of $\Delta = 5\%$ with a standard deviation of $\sigma = 7\%$.

This results in an expected maximum effect size of $(5-2)/7 = 3/7 = 0.43$ under conservative assumptions. Note that the threshold of clinical relevance is an absolute difference of 3% in the change from baseline over the placebo control group.

NT-proBNP: The following assumptions were made for the absolute change from baseline in the log-transformed NT-proBNP over 20 weeks:

- the expected mean effect under the placebo dose is assumed as an absolute decrease from baseline of $-0.105 \log(\text{pg/mL})$ with a standard deviation of $\sigma = 0.85 \log(\text{pg/mL})$, which is equivalent to a 10% relative reduction from a mean of 2,500 pg/mL at baseline.
- while the maximum observable mean effect under neladenoson bialanate within the dose range considered is assumed as an absolute decrease from baseline of $-0.357 \log(\text{pg/mL})$ with a standard deviation of $\sigma = 0.85 \log(\text{pg/mL})$, which is equivalent to a 30% relative reduction from a mean of 2,500 pg/mL at baseline.

It is assumed that the respective primary response efficacy variable, denoted as Y , is observed for the 6 parallel groups corresponding to doses levels: (placebo =) $d_1 < d_2 < \dots < d_k$, where $k = 6$.

For patient j within treatment group i the response can then be described by the following model:

$$Y_{ij} = f(d, \boldsymbol{\theta}) + \varepsilon_{ij}, \quad \varepsilon_{ij} \sim N(0, \sigma^2), \quad i = 1, \dots, k, \quad j = 1, \dots, n_i,$$

[figure not shown]
where $f(\cdot)$ is parameterized by a vector of parameters $\boldsymbol{\theta}$ and ε_{ij} is the error term.

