A “proof-of-concept” dose-response relationship is detected if at least one single contrast test, is statistically significant, while controlling the family-wise error rate at level α . The smallest of the corresponding adjusted p-values will be used for the Hochberg test.

This analysis will be performed for the FAS and PPS populations, where the PPS analysis is the primary analysis.

If no candidate model is statistically significant, the procedure stops, indicating that a dose-response relationship cannot be established from the observed data.

Out of the statistically significant models in the candidate set a best model can be selected for the next step: modeling and estimation.

Step 2: Modeling and estimation of target doses

If a dose-response signal is established, the selected dose-response model(s) will be fitted to the observed data to estimate the model parameters.

The estimated dose-response model will be plotted against the doses including 90% confidence bands. Once the dose-response model has been successfully fitted to the data, target dose(s) of interest are estimated. Given a clinically relevant effect Δ , a minimum effective dose (MED_{Δ}) associated with model $f(d, \theta)$ is defined as

$$MED_{\Delta} = \operatorname{argmin}_{d \in (d_1, d_6]} \{f(d, \theta) \geq f(d_1, \theta) + \Delta\}.$$

Estimates of MED_{Δ} will be calculated for a clinically relevant change in LVEF assumed as $\Delta = 3\%$ and potentially a plausible range of Δ values which will be defined in the SAP. Estimation for change in log-transformed NT-proBNP will be performed analogously, ensuring an adequate back-transformation to allow for better interpretability of the results. In addition, estimates considering confidence bounds for the predicted value at a certain dose may be used. The final choice of the target dose depends on the evaluation of the primary efficacy variables and other efficacy variables, as well as safety considerations.

Modeling and estimation will be performed for the FAS and PPS populations as well as for relevant subgroups.

Further details will be described in the SAP.

As a secondary analysis pairwise comparisons of the active neladenoson bialanate dose groups with the placebo group will be performed without controlling the family-wise error rate.

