4.5.4 Subgroup analyses

In order to assess the homogeneity of the dose response across the most important prognostic and predictive factors, subgroup analyses will be performed.

‘Key’ subgroups include:

- LVEF(%) at baseline: ≤ 25 vs. > 25
- LVEF(%) at baseline: ≤ 40 vs. > 40
- LVEF(%) at baseline: ≤ 45 vs. > 45
- NT-proBNP (pg/ml) at baseline: \leq median vs. $>$ median
- NYHA class at baseline: II vs. III / IV
- Prior β -blocker: yes vs. no

All other exploratory subgroups comprise demographic and baseline characteristics specified in section 6.1.2.

If the total number of subjects in a subgroup category is too small, the respective subgroup category will be either omitted from the analysis or combined with other categories, if a logical combination to another subgroup category is possible.

Prior hospitalization for heart failure is defined based on one of inclusion criterions.

CRF item (subject group) selected	Prior hospitalization (outpatients visit)
CHF Hospitalization/ unscheduled outpatient clinic visit with BNP/NTproBNP measurement in the last 3 months	Yes
Only BNP/NTproBNP measurement in the last 4 weeks	No
Combination of CHF Hospitalization/ unscheduled outpatient clinic visit with BNP/NTproBNP measurement in the last 3 months and additional measurement in the last 4 weeks	Yes

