- the expected mean effect under the placebo dose is assumed as an absolute decrease from baseline of $-0.105 \log(\text{pg/mL})$ with a standard deviation of $\sigma = 0.85 \log(\text{pg/mL})$, which is equivalent to a 10% relative reduction from a mean of 2,500 pg/mL at baseline.
- while the maximum observable mean effect under neladenoson bialanate within the dose range considered is assumed as an absolute decrease from baseline of $-0.357 \log(\text{pg/mL})$ with a standard deviation of $\sigma = 0.85 \log(\text{pg/mL})$, which is equivalent to a 30% relative reduction from a mean of 2,500 pg/mL at baseline.

It is assumed that the respective primary response efficacy variable, denoted as Y , is observed for the 6 parallel groups corresponding to doses levels: (placebo =) $d_1 < d_2 < \dots < d_k$, where $k = 6$.

For patient j within treatment group i the response can then be described by the following model:

$$Y_{ij} = f(d, \theta) + \varepsilon_{ij}, \quad \varepsilon_{ij} \sim N(0, \sigma^2), \quad i = 1, \dots, k, \quad j = 1, \dots, n_i,$$

[figure not shown]
where $f(\cdot)$ is parameterized by a vector of parameters θ and ε_{ij} is the error term.

A candidate set with $M=5$ different dose response shapes $f(\cdot)$ based on four models was chosen for the MCP-Mod method. Table 6–1 displays the response expressions for the shapes in the candidate sets for both, change in LVEF and change in log-transformed NT-proBNP. Figure 6–1 shows the corresponding dose-response shapes for change in LVEF. The model parameters were obtained through discussions with experts in the clinical team, taking prior beliefs and uncertainty into account. The dose-response shapes for NT-proBNP are equivalent to those for LVEF but with decreasing trends.

Table 6–1: Dose-response shapes used in the candidate set

Model	Response as function of dose d	
	LVEF	NT-proBNP
Linear	$2 + 0.075d$	$-0.105 - 0.0063d$
Sigmoidal E_{\max} 1	$2 + 3.007689d^4 / (9^4 + d^4)$	$-0.105 - 0.2526d^4 / (9^4 + d^4)$
Sigmoidal E_{\max} 2	$2 + 3.375d^3 / (20^3 + d^3)$	$-0.105 - 0.2835d^3 / (20^3 + d^3)$
E_{\max}	$2 + 3.09375d / (1.25 + d)$	$-0.105 - 0.2599d / (1.25 + d)$
Quadratic	$2 + 0.2d - 0.00333d^2$	$-0.105 - 0.0168d + 0.00028d^2$

Figure 6–1: Dose-response shapes used in the candidate set for change in LVEF

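### The key subgroup analyses are meant to assess homogeneity of the dose response, but no comparison between subgroup levels is prespecified

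*SAP*

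**What the plan says.** SAP 4.5.4, like Protocol 10.3.2.1, states the aim: "In order to assess the homogeneity of the dose response across the most important prognostic and predictive factors, subgroup analyses will be performed". The SAP lists six key entries: three cut-points of baseline LVEF (25, 40 and 45%), baseline NT-proBNP split at its median, NYHA class II against III/IV, and prior beta-blocker use.

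SAP 6.4.2 gives the method: primary, secondary and sensitivity "analyses (without imputed values) of primary efficacy variables will be performed based on key subgroups". For the remaining subgroups, "Additionally primary efficacy variables will be descriptively summarized based on exploratory subgroups". By SAP 6.2.1.2 the primary analysis is the two-step MCP-Mod procedure. By SAP 6.2.1.3 the secondary analysis is a set of 90% confidence intervals for each dose against placebo. Protocol 10.3.2.2 adds: "Modeling and estimation will be performed for the FAS and PPS populations as well as for relevant subgroups".

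Neither document mentions a dose-by-subgroup term, a difference between levels in any contrast, or a rule for reading two levels together. The adjusted analysis in SAP 6.2.1.5 lists covariates without interactions. The protocol leaves further subgroup detail to the SAP, which adds no comparison.

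**The concern.** Homogeneity is a statement about the difference between levels, and every planned analysis looks at one level at a time.

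The gap matters more because the repeated procedure is gated by significance. Under SAP 6.2.1.2, if no candidate contrast is significant, the procedure ends with the statement that no dose-response relationship could be shown. Curve fitting and target-dose estimation follow only after a signal. Applied within levels, one level can produce a fitted curve and a target dose while the other produces a negative statement, even when the true dose responses are the same. Each level is much smaller than the trial was sized for, so this will happen often if the drug works as planned.

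The trial is meant to guide Phase III. At stake is an unwarranted impression that the drug works in only one kind of patient.

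**Working it through.** **Inputs**
- Test level: "an overall one-sided type I error level of 5% is planned to be used" (Protocol 10.3.2).
- LVEF: placebo change 2%, maximum 5%, SD 7%. "This results in an expected maximum effect size of $(5-2)/7 = 3/7 = 0.43$ under conservative assumptions" (Protocol 10.3.2.2).
- NT-proBNP: log change −0.105 on placebo and −0.357 at maximum, SD 0.85; the latter is a change "which is equivalent to a 30% relative reduction from a mean of 2,500 pg/mL at baseline" (SAP 6.2.1.2).
- Five candidate shapes (SAP Table 6–1) and allocation 3:1:2:2:2:2 for 0, 5, 10, 20, 30 and 40 mg.
- 288 evaluable patients of 384 randomized (Protocol 10.4).
- Split: 50:50 by design only for the NT-proBNP median. All other splits are assumptions.

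**Step 1: reproduce the plan's figures.** Contrasts proportional to n_i(μ_i − μ̄), scaled to unit length, match SAP Table 6–2 to 0.001. The critical value is the 95th percentile of the maximum of the five correlated t statistics with N − 6 degrees of freedom (1.965 at N = 288). Simulated power agrees with Protocol Table 10–2 (first two columns below).

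**Step 2: run the same test in each half (144 patients: 36, 12, 24, 24, 24, 24), with the same true LVEF curve in both.** With power p per half, P(exactly one significant) = 2p(1 − p) and P(both significant) = p². For the linear shape, 2 × 0.542 × 0.458 = 0.497; for sigmoidal Emax 1, 2 × 0.678 × 0.322 = 0.437.

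| Shape | Power at 288, Table 10–2 | Recomputed | Power per half | Exactly one significant | Both significant |
|---|---|---|---|---|---|
| Linear | 80.31% | 80.2% | 54% | 49.7% | 29% |
| Sigmoidal Emax 1 | 91.39% | 91.3% | 68% | 43.7% | 46% |
| Sigmoidal Emax 2 | 87.30% | 87.4% | 62% | 47.2% | 38% |
| Emax | 88.25% | 88.1% | 63% | 46.7% | 40% |
| Quadratic | 86.09% | 86.0% | 61% | 47.7% | 37% |

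**Step 3: vary the assumptions.** For unequal levels, P(exactly one) = p₁(1 − p₂) + p₂(1 − p₁).
- LVEF, 70:30 (203 and 85 patients): power is 67–81% and 38–49%. Linear: 0.67 × 0.62 + 0.38 × 0.33 = 0.54. Sigmoidal Emax 1: 0.81 × 0.51 + 0.49 × 0.19 = 0.51. Range 51–54%.
- LVEF, 20:80: 59–60%. LVEF, 10:90: 67–71%.
- LVEF, 50:50, all 384 evaluable: 33–46%.
- NT-proBNP, 50:50 of 288: power per half 33–42%, exactly one significant in 44–49%.
- No effect in either half: 2 × 0.05 × 0.95 = 0.095, about 10%.

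**Step 4: what a between-level contrast would do.** If the dose response is the same in both levels, a 90% interval for the difference excludes zero in 10% of trials, its nominal rate. Now suppose the whole planned LVEF effect sits in one 50:50 half. The within-half standardized contrast is √(Σn_i(μ_i − μ̄)²)/σ. For the linear shape this is √170.3/7 = 1.864. The difference between halves has √2 times the standard error, so power at two-sided 10% is Φ(1.864/√2 − 1.645) = Φ(−0.327) = 37%. For sigmoidal Emax 1 it is Φ(2.221/√2 − 1.645) = 47%. The other shapes fall between, giving 37–47%; at two-sided 5% the range is 26–35%.

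**The case against.** Several points on the other side are sound.

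- **No decision rule is stated.** A reader might infer that the SAP will judge homogeneity by comparing significance across levels. It does not say so. It states an aim, lists within-level analyses, and is silent on how to compare them.
- **Estimates are planned too.** The repeated secondary analysis gives pairwise 90% intervals in every level, whatever the test result. The levels contain different patients, so a between-level difference for each dose could be derived from that output. It would therefore be too strong to say that the planned analyses cannot address homogeneity. What is missing is a prespecified and displayed comparison.
- **Disagreement in about half of trials is not general.** It needs the full planned effect and 288 evaluable patients. Zero effect in both levels is also homogeneous, and there the figure is about 10%.
- **The figure does not carry over to six factors.** Three entries are cut-points of one variable, leaving four distinct factors. Entry requires LVEF of 35% or less, and patients should be on standard therapy including beta-blockers, so several levels may be small. SAP 4.5.4 allows small categories to be omitted or combined.
- **The consequence is limited.** The subgroup analyses carry no type I error control, and neither document ties the Phase III population to a subgroup p-value. The target dose rests on the primary and other efficacy variables and on safety.
- **Part of the plan is unseen.** SAP 6.2.1.5 refers to a separate TLF specification, which might hold further subgroup displays.

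These limit the wording and the size of the point. They do not supply the missing comparison, which belongs in the SAP because the SAP states the aim.

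**Conclusion.** The point holds in this form: the SAP sets a homogeneity aim for the key subgroups, plans only within-level analyses, and prespecifies no comparison between levels. Because the MCP step gates curve fitting, levels with identical true effects can be reported differently. For LVEF at the planned effect, one-sided 5%, 288 evaluable patients and a 50:50 split, this happens in 44–50% of trials; at an assumed 70:30 split, in 51–54%. Actual splits other than the NT-proBNP median are not given in the documents. The primary test and its error control are untouched, so the change is advisable rather than essential to the trial's main conclusion.

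**What to change.** Add to SAP 6.4.2, for each distinct key factor whose levels are of adequate size (minimum size to be stated):

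1. Fit one model with dose group, subgroup and their interaction, for each primary variable.
2. Report the between-level difference in the optimal-contrast estimate, for the selected shape or for each shape, with a 90% confidence interval. Use the same contrast coefficients in both levels. Coefficients updated to each level's own group sizes would differ, and the two estimates would not be directly comparable.
3. Label the result exploratory, and state that homogeneity is described from this estimate and interval, not from which levels reach significance.
4. For baseline LVEF, name one cut-point for this comparison, since the three listed are not separate factors.

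The cost is one extra model per factor and variable, with no new data and no change to the primary analysis. The drawback is imprecision: with 37–47% power at two-sided 10% even when the whole planned LVEF effect sits in one half, an interval that includes zero must not be read as proof of homogeneity. For the same reason the interval should lead, and an interaction p-value adds little.

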6.4.3 Subgroup analysis of safety variables

Incidence rate of treatment-emergent AEs and treatment-emergent ECG abnormalities not presented at baseline (by AVIVO and HealthPatch, Japan only) will be summarized based on key and exploratory subgroups.

6.5 Pharmacokinetics/pharmacodynamics

Pharmacokinetic analyses will be performed on the population valid for pharmacokinetics.

For the investigation of systemic exposure to BAY 84-3174 and its relationship with treatment effects, the plasma concentrations of BAY 84-3174 will be determined at different time points using a sparse sampling approach in all participating patients (see Clinical Study Protocol Section 9.5). The plasma concentration vs. time data will be evaluated descriptively separated by dose and visit. Plots will be prepared pooling all individual plasma concentrations (naive pooling) vs. actual relative study times (time of sample collection after time of study drug administration).

Furthermore, the pharmacokinetic data and the relationship of markers of BAY 84-3174 exposure (e.g. C_{max} , AUC) with treatment effects will be evaluated using non-linear mixed effect modeling (NONMEM). The latter evaluation will be described in a separate analysis plan and will be reported under separate cover.

The PK bioanalysis will be performed under the responsibility of the Sponsor’s Bioanalytics Laboratory.

6.6 Biomarker analyses

Biomarker data will be described by the following summary statistics: arithmetic mean, standard deviation, median, quantiles, minimum, and maximum.

Box plots and line plots of means of biomarkers over visits, by treatment group will be provided. Additional analyses of safety and efficacy biomarkers and their results will be provided in a separate report.

7. Document history and changes in the planned statistical analysis

Version	Date	Action
Version 1.0	13Nov2017	
Version 2.0	19 April 2018	
 • Change the wording in section 6.3.6 • Add more detailed description of plots we plan to provide in section 6.6
Version 3.0	29 May 2018	
 • Add one more key subgroup: LVEF(%) at baseline: ≤45 vs. >45 • Add more details of worst case imputation and censoring rule of time to event variables in section 6.2 • Some minor changes in subgroup

		
analyses in section 6.4
 
 Remove some unused variables from Appendix 9.1
--	--	---

8. References

3. Executive summary: HFSA 2006 Comprehensive Heart Failure Practice Guideline. *J Card Fail*. 2006;12(1):10-38.
8. Rubin DB. Multiple imputation for nonresponse in surveys. New York: Wiley; 1987.

9.1 AVIVO device variable specification

In the following, we describe the variables which will be analyzed

- **Activity**

Variable	Summary measure(s)	Unit	Length of intervals
activity duration	duration	seconds	daily
activity intensity	mean	mG	1 hour
activity intensity	mean, max	%	daily

- **Notifiable findings**

These should be the findings that trigger a **notifiable report**, definitions as below:

Finding	Notification criteria
Ventricular fibrillation	always notified
ICD discharge	always notified
Ventricular Tachycardia	any rate and ≥ 10 beats
Wide complex Tachycardia	any rate and ≥ 10 beats
PVCs	never notified
Sinus Bradycardia	≤ 30 bpm
Sinus Tachycardia	≥ 180 bpm
Supraventricular tachycardia	≥ 150 bpm AND ≥ 30 sec
A. Fibrillation or A. flutter	≥ 150 bpm AND ≥ 30 sec
A. Fibrillation or A. flutter	≤ 30 bpm and ≥ 30 sec
A. Fibrillation or A. flutter	when notification criteria are met
pause	≥ 3.0 sec
AV block 2nd (Mobitz I)	≤ 50 bpm
AV block 2nd (Mobitz II)	always notified
Isolated 2nd degree AV block (2:1)	≤ 50 bpm
High degree AV block	always notified

3rd Degree AV block	always notified
other	
Patient triggered Events	when notification criteria are met
Technicians discretion	any

